#### **9.4.3 Handling of missing values/censoring/discontinuations**

Missing data will be imputed using the last-observation-carried-forward (LOCF) method. If a subject has no post-baseline value, the missing value will not be imputed and the subject will be removed from the analysis. If a subject's data is missing or unevaluable for the week preceding randomization, the data from the previous week will be used as the baseline measurement. If a subject's data is missing or unevaluable for each of these weeks, the subject will be excluded from the analysis.

#### **9.4.4 Sensitivity analyses**

A supportive nonparametric analysis will be performed to examine the consistency of results. For this supportive analysis, the primary efficacy variable will be analyzed using the Wilcoxon rank-sum test. The probability of one treatment being better than the other treatment will be estimated (based on the Wilcoxon rank-sum test) and the associated 95% confidence interval will be reported ([Chen and Kianifard 2000](#)).

### **9.5 Analysis of secondary variables**

#### **9.5.1 Efficacy variables**

The secondary efficacy variables are the following assessments defined based on actigraphy data:

- Change in mean activity (counts per minute) during sleep between baseline phase and week 8 (Randomized treatment phase)
- Change in mean activity during sleep between baseline phase and week 1 (Randomized treatment phase)
- Change in mean activity during sleep between baseline phase and week 9 and 16 (Open label extension phase)
- Change in mean activity counts during the most active 30 minutes of the subject's day between baseline phase and week 1 (Randomized treatment phase)
- Change in mean activity counts during the most active 30 minutes of the subject's day between baseline phase and week 9 and 16 (Open label extension phase)

During the randomized treatment phase, mean change from baseline for each continuous variable will be analyzed at each time point using the same ANCOVA model as for the primary efficacy variable, and missing data will be imputed using the LOCF method.

During the open label extension phase, change from baseline (mean of week -1) for each continuous variable will be analyzed at each time point using paired t-tests for the group randomized to sacubitril/valsartan. The analyses will be repeated using the week 8 measurement as baseline for the group randomized to Enalapril.

### **9.5.2 Safety variables**

The safety and tolerability assessments are listed below:

- AEs and SAEs
- Sitting systolic, diastolic BP, and pulse pressure
- Heart rate
- Laboratory values

The assessment of safety will be based primarily on the frequency of adverse events, SAEs, and laboratory abnormalities. Other safety data will be summarized as appropriate.

The incidence of treatment-emergent adverse events (new or worsened) will be summarized by primary system organ class, preferred term, severity, and relationship to study drug. In addition, the incidence of death, SAEs, and AEs leading to discontinuation will be summarized separately by primary system organ class and preferred term.

Laboratory data will be summarized by presenting shift tables using extended reference ranges (baseline to most extreme post-baseline value), by presenting summary statistics of raw data and change from baseline values (mean, median, standard deviation, 25th and 75th percentiles, interquartile range, minimum and maximum) and by the flagging of notable values in data listings.

Data from other tests will be listed, notable values will be flagged, and any other information collected will be listed as appropriate.

Safety analyses will be performed based on the Safety Set. There will be no inferential analyses of the safety data.

### **9.5.3 Resource utilization**

Not Applicable.

### **9.5.4 Pharmacokinetics**

Not Applicable.

### **9.5.5 DNA**

[figure not shown]
Not Applicable.

[figure not shown]
### **9.5.6 Biomarkers**

Not Applicable.

### **9.5.7 PK/PD**

Not Applicable.

## **9.7 Interim analyses**

Not applicable.

## **9.8 Sample size calculation**

Primary endpoint:

Assuming a significance level of 0.05, a total sample size of 136 subjects would provide 90% power to detect a difference of 5000 in the change from baseline in mean activity counts collected during the most active 30 minutes between the sacubitril/valsartan treatment group and the enalapril group during Week 8, assuming a common standard deviation of 7400 (Maurer 2009) and a 20% drop-out rate and a 10% rate of subjects with non-evaluable data. The assumed effect size of 68% (5000/7400) will be maintained in the event the log transformation is needed for the primary analysis thus not affecting the sample size calculation and power of the study.

Secondary endpoint:

Assuming a significance level of 0.05, a sample size of 136 subjects would provide 93% power to detect a 3.5 point difference in the change from baseline in mean activity value during the sleep (expressed as counts per minute) between the sacubitril/valsartan treatment group and the enalapril group during Week 8, assuming a common standard deviation of 4.9 and a 20% drop-out rate and a 10% rate of subjects with non-evaluable data (Peterson 2012).

## 10 Ethical considerations

### 10.1 Regulatory and ethical compliance

This clinical study was designed and shall be implemented, executed and reported in accordance with the ICH Harmonized Tripartite Guidelines for Good Clinical Practice, with applicable local regulations (including European Directive 2001/20/EC, US CFR 21, and Japanese Ministry of Health, Labor, and Welfare), and with the ethical principles laid down in the Declaration of Helsinki.

### 10.2 Informed consent procedures

Eligible subjects may only be included in the study after providing written (witnessed, where required by law or regulation), IRB/IEC-approved informed consent, or, if incapable of doing so, after such consent has been provided by a legally acceptable representative(s) of the subject. In cases where the patient's representative gives consent, the subject must be informed about the study to the extent possible given his/her understanding. If the patient is capable of doing so, he/she must indicate assent by personally signing and dating the written informed consent document or a separate assent form. Informed consent must be obtained before conducting any study-specific procedures (e.g. all of the procedures described in the protocol). The process of obtaining informed consent must be documented in the patient source documents.

Novartis will provide to investigators in a separate document a proposed informed consent form that complies with the ICH GCP guideline and regulatory requirements and is considered appropriate for this study. Any changes to the proposed consent form suggested by the investigator must be agreed to by Novartis before submission to the IRB/IEC, and a copy of the approved version must be provided to the Novartis monitor after IRB/IEC approval.

Women of child bearing potential must be informed that taking the study treatment may involve unknown risks to the fetus if pregnancy were to occur during the study and agree that in order to participate in the study they must adhere to the contraception requirement for the duration of the study. If there is any question that the patient will not reliably comply, they must not be entered in the study.

### 10.3 Responsibilities of the investigator and IRB/IEC

Before initiating a trial, the investigator/institution must obtain approval/favorable opinion from the Institutional Review Board/Independent Ethics Committee (IRB/IEC) for the trial protocol, written informed consent form, consent form updates, subject recruitment procedures (e.g., advertisements) and any other written information to be provided to subjects. Prior to study start, the investigator is required to sign a protocol signature page confirming his/her agreement to conduct the study in accordance with these documents and all of the instructions and procedures found in this protocol and to give access to all relevant data and records to Novartis monitors, auditors, Novartis Quality Assurance representatives, designated agents of Novartis, IRBs/IECs, and regulatory authorities as required. If an inspection of the clinical site is requested by a regulatory authority, the investigator must inform Novartis immediately that this request has been made.

## **10.4 Publication of study protocol and results**

The key design elements of this protocol will be posted in a publicly accessible database such as clinicaltrials.gov. In addition, upon study completion and finalization of the study report the results of this trial will be either submitted for publication and/or posted in a publicly accessible database of clinical trial results.

## **10.5 Quality Control and Quality Assurance**

Novartis maintains a robust Quality Management (QM) system that includes all activities involved in quality assurance and quality control, including the assignment of roles and responsibilities, the reporting of results, and the documentation of actions and escalation of issues identified during the review of quality metrics, incidents, audits and inspections.

Audits of investigator sites, vendors, and Novartis systems are performed by Novartis Pharma Auditing and Compliance Quality Assurance, a group independent from those involved in conducting, monitoring or performing quality control of the clinical trial. The clinical audit process uses a knowledge/risk based approach.

Audits are conducted to assess GCP compliance with global and local regulatory requirements, protocols and internal SOPs, and are performed according to written Novartis processes.

## **11 Protocol adherence**

This protocol defines the study objectives, the study procedures and the data to be collected on study participants. Additional assessments required to ensure safety of subjects should be administered as deemed necessary on a case by case basis. Under no circumstances is an investigator allowed to collect additional data or conduct any additional procedures for any research related purpose involving any investigational drugs under the protocol.

Investigators ascertain they will apply due diligence to avoid protocol deviations. If an investigator feels a protocol deviation would improve the conduct of the study this must be considered a protocol amendment, and unless such an amendment is agreed upon by Novartis and approved by the IRB/IEC and health authorities, where required, it cannot be implemented.

### **11.1 Protocol amendments**

Any change or addition to the protocol can only be made in a written protocol amendment that must be approved by Novartis, health authorities where required, and the IRB/IEC prior to implementation. Only amendments that are intended to eliminate an apparent immediate hazard to subjects may be implemented immediately provided the health authorities are subsequently notified by protocol amendment and the reviewing IRB/IEC is notified. Notwithstanding the need for approval of formal protocol amendments, the investigator is expected to take any immediate action required for the safety of any subject included in this study, even if this action represents a deviation from the protocol. In such cases, the reporting requirements identified in Section 7 Safety Monitoring must be followed.

## 13 Appendix 1: Clinically notable laboratory values and vital signs

Clinically notable laboratory abnormalities for selected tests based on a percent change from baseline:

### Hematology

RBC count	>50% increase, >20% decrease
Hemoglobin	>50% increase, >20% decrease
Hematocrit	>50% increase, >20% decrease
WBC count	>50% increase, >50% decrease
Platelet count	>75% increase, >50% decrease

### Blood Chemistry

ALT (SGPT)	>150% increase
AST (SGOT)	>150% increase
BUN	>50% increase
Creatinine	>50% increase
Total bilirubin	>100% increase
Alkaline phosphatase	>100% increase
Potassium	>20% increase, >20% decrease
Chloride	>10% increase, >10% decrease
Calcium	>10% increase, >10% decrease
Uric acid	>50% increase

## 14 Appendix 2: Liver event and Laboratory trigger Definitions and Follow-up Requirements

**Table 14-1 Liver Event and Laboratory Trigger Definitions**

	Definition/ threshold
LIVER LABORATORY TRIGGERS	 $3 \times \text{ULN} < \text{ALT} / \text{AST} \leq 5 \times \text{ULN}$  $1.5 \times \text{ULN} < \text{TBL} \leq 2 \times \text{ULN}$
LIVER EVENTS	 ALT or AST $> 5 \times \text{ULN}$  ALP $> 2 \times \text{ULN}$ (in the absence of known bone pathology)  TBL $> 2 \times \text{ULN}$ (in the absence of known Gilbert syndrome)  ALT or AST $> 3 \times \text{ULN}$ and INR $> 1.5$  Potential Hy's Law cases (defined as ALT or AST $> 3 \times \text{ULN}$ and TBL $> 2 \times \text{ULN}$ [mainly conjugated fraction] without notable increase in ALP to $> 2 \times \text{ULN}$ )  Any clinical event of jaundice (or equivalent term)  ALT or AST $> 3 \times \text{ULN}$ accompanied by (general) malaise, fatigue, abdominal pain, nausea, or vomiting, or rash with eosinophilia  Any adverse event potentially indicative of a liver toxicity*

\*These events cover the following: hepatic failure, fibrosis and cirrhosis, and other liver damage-related conditions; the non-infectious hepatitis; the benign, malignant and unspecified liver neoplasms

TBL: total bilirubin; ULN: upper limit of normal

**Table 14-2 Follow Up Requirements for Liver Events and Laboratory Triggers**

Criteria	Actions required	Follow-up monitoring
Potential Hy's Law case a	 Discontinue the study treatment immediately  Hospitalize, if clinically appropriate  Establish causality 	ALT, AST, TBL, Alb, PT/INR, ALP and γGT until resolution c (frequency at investigator discretion)
ALT or AST		
> 8 × ULN	 Discontinue the study treatment immediately  Hospitalize if clinically appropriate  Establish causality 	ALT, AST, TBL, Alb, PT/INR, ALP and γGT until resolution c (frequency at investigator discretion)
> 3 × ULN and INR > 1.5	 Discontinue the study treatment immediately  Hospitalize, if clinically appropriate  Establish causality 	ALT, AST, TBL, Alb, PT/INR, ALP and γGT until resolution c (frequency at investigator discretion)
> 5 to ≤ 8 × ULN	 Repeat LFT within 48 hours  If elevation persists, continue follow-up monitoring  If elevation persists for more than 2 weeks, discontinue the study drug  Establish causality 	ALT, AST, TBL, Alb, PT/INR, ALP and γGT until resolution c (frequency at investigator discretion)
> 3 × ULN accompanied by symptoms b	 Discontinue the study treatment immediately  Hospitalize if clinically appropriate  Establish causality 	ALT, AST, TBL, Alb, PT/INR, ALP and γGT until resolution c (frequency at investigator discretion)
> 3 to ≤ 5 × ULN (patient is asymptomatic)	 Repeat LFT within the next week  If elevation is confirmed, initiate close observation of the patient	Investigator discretion Monitor LFT within 1 to 4 weeks
ALP (isolated)		
> 2 × ULN (in the absence of known bone pathology)	 Repeat LFT within 48 hours  If elevation persists, establish causality 	Investigator discretion Monitor LFT within 1 to 4 weeks or at next visit
TBL (isolated)		

Criteria	Actions required	Follow-up monitoring
> 2 × ULN (in the absence of known Gilbert syndrome)	 Repeat LFT within 48 hours  If elevation persists, discontinue the study drug immediately  Hospitalize if clinically appropriate  Establish causality 	ALT, AST, TBL, Alb, PT/INR, ALP and γGT until resolution c (frequency at investigator discretion) Test for hemolysis (e.g., reticulocytes, haptoglobin, unconjugated [indirect] bilirubin)
> 1.5 to ≤ 2 × ULN (patient is asymptomatic)	 Repeat LFT within the next week  If elevation is confirmed, initiate close observation of the patient	Investigator discretion Monitor LFT within 1 to 4 weeks or at next visit
Jaundice	 Discontinue the study treatment immediately  Hospitalize the patient  Establish causality 	ALT, AST, TBL, Alb, PT/INR, ALP and γGT until resolution c (frequency at investigator discretion)
Any AE potentially indicative of a liver toxicity*	 Consider study treatment interruption or discontinuation  Hospitalization if clinically appropriate  Establish causality 	Investigator discretion

aElevated ALT/AST > 3 × ULN and TBL > 2 × ULN but without notable increase in ALP to > 2 × ULN

b(General) malaise, fatigue, abdominal pain, nausea, or vomiting, or rash with eosinophilia

cResolution is defined as an outcome of one of the following: (1) return to baseline values, (2) stable values at three subsequent monitoring visits at least 2 weeks apart, (3) remain at elevated level after a maximum of 6 months, (4) liver transplantation, and (5) death.

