#### **5.5.4 Instructions for prescribing and taking study treatment**

Novartis will supply the investigators with all medications sufficient for the course of the study. Subjects will be provided with medication packs containing study drug corresponding to their assigned treatment arm and dose level, sufficient to last until the next scheduled visit. Study medication should be taken with a glass of water with or without food. If the patient misses taking any study drug dose, he/she should take it as soon as possible, unless it is within 4 hours for the following scheduled dose. In this case, the patient should skip the missed dose and return back to his/her regular study drug administration schedule.

In order to adequately blind the study, patients will be required to take their assigned active treatment tablet along with placebo matching the opposite treatment twice daily. Subjects will be instructed to take a total of two tablets by mouth twice a day for the duration of the double-blind treatment epoch, as follows:

- One tablet from the sacubitril/valsartan – sacubitril/valsartan matching placebo pack, and;
- One tablet from the enalapril - enalapril matching placebo pack

[Table 5-5](#) summarizes the study drug that will be taken during the double-blind treatment epoch by visit and [Table 5-6](#) summarizes the study drug that will be taken during the open-label treatment epoch.

Forced-titration will proceed according to the following table:

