#### **6.5.5.2 Clinical chemistry**

Blood urea nitrogen (BUN), glucose, creatinine, total bilirubin, AST (SGOT), ALT (SGPT), alkaline phosphatase, sodium, potassium, chloride, calcium, hemoglobin A1C, total protein, albumin, uric acid, and lipid profile will be measured at all visits 1, 3, 5, 8, 10, and 13 (central lab).

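### Table 14-2 gives bilirubin above 2 × ULN a weaker stopping rule when ALT/AST and ALP are also raised than when bilirubin is raised alone

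*Protocol*

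**What the plan says.** Protocol Appendix 2 has two tables. Table 14-1 defines liver events. One is TBL above 2 × ULN, qualified only by "in the absence of known Gilbert syndrome". It does not require the other liver tests to be normal.

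Table 14-2 sets the actions. As a laboratory value, TBL above 2 × ULN appears in two places:

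- **Potential Hy's Law case** (stop immediately). Footnote a defines it as "Elevated ALT/AST > 3 × ULN and TBL > 2 × ULN but without notable increase in ALP to > 2 × ULN". Table 14-1 carries the same limit: "without notable increase in ALP to" above 2 × ULN.
- **TBL rows, headed as isolated.** Above 2 × ULN, liver tests are repeated within 48 hours, then: "If elevation persists, discontinue the study drug immediately".

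The ALT/AST rows that bear on this point are:

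- Above 3 and up to 5 × ULN, asymptomatic: "Repeat LFT within the next week", then close observation if confirmed. There is no stopping rule.
- Above 5 and up to 8 × ULN: repeat within 48 hours, then: "If elevation persists for more than 2 weeks, discontinue the study drug".
- Above 8 × ULN, or above 3 × ULN with INR above 1.5 or with listed symptoms: stop immediately.

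The ALP row is also limited to isolated elevation and contains no stopping rule. Nothing in the table says which row governs when several apply.

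**The concern.** Footnote a takes a patient with raised ALP out of Hy's Law, and the heading of the TBL rows takes a patient with other raised liver tests out of the bilirubin rule. A patient with all three raised is left with the ALT/AST rows alone, which were written without regard to bilirubin.

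Removing a mixed pattern from Hy's Law may well be deliberate. That does not explain an action weaker than the one for bilirubin alone. With ALT at 4 and TBL at 2.5 × ULN, moving ALP from just below to just above 2 × ULN changes the written action from an immediate stop to observation.

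This is a safety rule that applies in both the blinded and open-label phases. The protocol has no data monitoring committee (Section 8.4), and no exclusion criterion sets a liver-test threshold (Section 4.2).

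**Working it through.** The plan gives no figure to reproduce here, so the check applies Table 14-2 row by row.

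**Set-up.** ALT/AST in four bands (≤3, >3–5, >5–8, >8 × ULN), TBL in three (≤1.5, >1.5–2, >2) and ALP in two (≤2, >2) give 4 × 3 × 2 = 24 combinations, of which 4 × 2 = 8 have TBL above 2 × ULN. The check assumes no symptoms, jaundice, liver adverse event, INR above 1.5, Gilbert syndrome or bone pathology.

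**Ordering of actions (made for this check).** 0 = no row; 1 = retest within 7 days, no stop; 2 = retest within 48 hours, no stop; 3 = retest within 48 hours, stop if it lasts more than 2 weeks; 4 = retest within 48 hours, stop at once if persistent; 5 = stop now. Isolated TBL above 2 × ULN scores 4.

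**Two readings of isolated.** A: no ALT/AST elevation. B: no other liver test raised.

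| ALT/AST (× ULN), with TBL >2 | ALP ≤2 | ALP >2 |
|---|---|---|
| ≤3 | 4 | 4 (A) or 0 (B) |
| >3–5 | 5 (Hy's Law) | **1** |
| >5–8 | 5 (Hy's Law) | **3** |
| >8 | 5 | 5 |

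Two of the 8 combinations score below 4 under reading A and three under reading B. The two bold cells are the same under both.

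**Delay on drug.** In the double-blind phase, Section 5.5.4 has patients "take a total of two tablets by mouth twice a day", which is two dosing times a day.

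- ALT/AST >5–8: the stop comes after day 14 instead of at the 48-hour retest. (14 − 2) = 12 days; 12 × 2 = 24 doses, as a minimum.
- ALT/AST >3–5: the retest can come up to (7 − 2) = 5 days later; 5 × 2 = 10 doses. No stop follows.

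**INR as a backstop.** The scheduled chemistry in Section 6.5.5.2 includes "total bilirubin, AST (SGOT), ALT (SGPT), alkaline phosphatase, sodium, potassium, chloride, calcium, hemoglobin A1C, total protein, albumin, uric acid, and lipid profile" but no INR. Follow-up in the >3–5 row is left to the investigator and names only liver tests. In the >5–8 row, follow-up does include PT/INR, but it changes the action only if INR exceeds 1.5.

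**Expected frequency.** The documents give no incidence. Assume that 0.05% to 0.5% of patients reach this profile.

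- Expected number: 136 × 0.0005 = 0.07; 136 × 0.005 = 0.68.
- Chance of at least one, 1 − (1 − p)^136: 6.6% and 49.4%.

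**After the change.** If the TBL row applies to any TBL above 2 × ULN and the strictest applicable row governs, the bold cells become 4 and the ≤3 cell with ALP >2 is 4 under either reading. None of the 8 is then weaker than isolated TBL.

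**The case against.** The strongest reply is a third reading: isolated might mean only *not a Hy's Law case*. Table 14-1 supports it, because it lists TBL above 2 × ULN as a liver event without that limit, and Table 14-2 is the follow-up table for those events. On this reading the inversion disappears. But it needs the reader to set aside the row's own heading, and no line in the table tells the investigator to do so.

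Other safeguards exist. Section 5.6.2 requires discontinuation once the investigator believes that continuing may be detrimental. An abnormal result judged clinically significant counts as an adverse event (Section 7.1), which could bring in the liver-toxicity row. Fatigue is a listed symptom and is common in heart failure, so some patients would meet the immediate-stop row. These soften the practical effect. However, the first depends on judgment, the liver-toxicity row only asks the investigator to consider stopping and its footnote lists hepatic diagnoses, and the last leaves asymptomatic patients where they were.

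Some action cells, including the >5–8 row, end in a blank item that may be removed text. The stopping rules themselves are legible, and the >3–5 row has no blank item, so that comparison does not depend on missing text.

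It is also true that the profile is rare, that the incidence range is only an assumption, and that counting cells does not weight them by likelihood. This limits the expected consequence but does not correct the rule.

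**Conclusion.** The concern holds as written. For ALT/AST above 3 and up to 8 × ULN with TBL and ALP both above 2 × ULN, the written action is weaker than for TBL above 2 × ULN alone, under either of the two readings in the check. In the lower band there is no stopping rule; in the upper, the stop comes at least 12 days later. With ALT/AST at or below 3 × ULN there is also a gap, but only if isolated means that no other liver test is raised.

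The conclusion rests on taking the heading at face value and on the absence of symptoms, jaundice, a liver adverse event and INR above 1.5. Under the assumed incidence, fewer than one patient of 136 is expected. The sample size is unaffected and the primary analysis essentially so: Visit 5 is the only scheduled post-dose chemistry before Visit 8. The table should be corrected because it is a safety stopping rule and the correction is a matter of wording.

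**What to change.** Remove the isolated limit from the TBL above 2 × ULN row, so that its 48-hour retest and immediate stop on persistence become the minimum for any such value without known Gilbert syndrome. Leave the Hy's Law row as the stricter rule.

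Add one line under Table 14-2: *If more than one row applies, the most stringent action governs.* This also settles the case where a patient meets both the >5 to ≤8 × ULN row and the row for ALT/AST above 3 × ULN with symptoms.

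The cost is one heading and one added line. No test, visit or patient is added. The downside is possibly slightly more early discontinuations.
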